4.1.3 Analysis Populations

The analysis populations defined for this study are presented in [Table 4-1](#).

Table 4-1 Analysis Populations

Population	Definition / Criteria	Analyses Evaluated
Safety	Comprise all randomized subjects who complete at least one use of study product. This population will be based on the product the subject actually received.	Safety Analysis
Modified Intent-To-Treat (mITT)	Comprise all randomized subjects who have a post-baseline plaque assessment. This population will be based on the product to which the subject was randomized. Any subject who receives a randomization number will be considered to have been randomized.	Demographic and Baseline Characteristics, Efficacy Analysis
RPI Repeatability	Comprise all subjects who have a repeat clinical efficacy assessment for RPI index at any visit.	Exploratory Repeatability Analyses
TPI Repeatability	Comprise all subjects who have a repeat clinical efficacy assessment for TPI index at any visit.	Exploratory Repeatability Analyses

NOTE:

Please refer to [Attachment 1](#): List of Data Displays which details the population to be used for each displays being generated.

Due to the exploratory nature of the study, the Per Protocol population will not be defined. The primary population for assessment of efficacy will be the mITT population. Repeatability Population will be used only to support repeatability analyses.

The numbers of subjects included in each of the analysis populations will be presented in [Table 14.1.1](#) by study product group and overall. Subjects excluded from any of the analysis populations will be listed in [Listing 16.2.3.1](#) by study product group.

4.2 Subject Demographics and Other Baseline Characteristics

Demographic and baseline characteristics summaries will be produced for the mITT.

4.2.1 Demographic Characteristics

Descriptive statistics (number of subjects [n], mean, standard deviation [SD], median, minimum and maximum for continuous variables and frequency count [n] and percentage [%] of subjects for categorical variables) will be presented for demographic variables by study product group and overall. These variables include age, gender and race and will be presented for mITT population (Table 14.1.3). In addition, stratification groups defined as Day 0 pre-brushing mean RPI_{gingival/interproximal} score (categorized as: lower - mean RPI_{gingival/interproximal} ≥ 0.6 to ≤ 0.8 ; and higher - mean RPI_{gingival/interproximal} > 0.8 to 1.0) will also be summarized for mITT population (Table 14.1.3).

Demographic information will be listed (Listing 16.2.4.1) for all randomized subjects by study product group.

4.2.2 General Medical History

Medical history data will be listed (Listing 16.2.4.2) for all randomized subjects with start date and end date or ongoing at the start of the study.

4.3 Treatments (Study Product, Rescue Medication, other Concomitant Therapies, Compliance)

The study product kit allocations will be listed (Listing 16.1.6.1), including kit number and study product information.

Randomization details will be listed, including the randomization number, stratification group, planned randomized study product, actual study product and the randomization date (Listing 16.1.7.1).

4.3.1 Study Product Compliance and Exposure

To promote compliance throughout the study, subjects will be provided with a diary at Screening (Visit 1) and at Baseline (Visit 2) to record each brushing with their lead-in toothbrush and study toothbrush respectively. They will also use the diary to note any missed/additional brushings, the reasons for any missed/additional brushings, any issues with the toothbrush or toothpaste used, oral problems, illnesses and any new medications/treatments. Subjects will attend each study visit with the lead-in/study products provided (used and unused) for a visual check of product usage, and with their completed diary for review by study staff.

Subjects will be instructed to self-perform oral hygiene with the lead-in toothbrush and their assigned study toothbrush (using the regular fluoride toothpaste provided) according to the usage instructions provided at the study site and detailed in the diary.

A supervised brushing will be carried out at the study site at the end of Visit 1 to facilitate subject compliance with brushing instructions and diary completion. Other on-site brushings (Visits 2-4) will be carried out in the presence of study staff but will not be supervised.

The number of missed or additional brushings will be captured as protocol deviations and transcribed from the diary into the eCRF. Subjects will be re-instructed in the correct usage requirements and diary completion as needed.

No summaries of lead-in product compliance will be provided.

Study product compliance data will be summarized for the mITT population in [Table 14.2.1.1](#). Total number of brushings, compliance (%), number of missed brushings and number of additional brushings will be summarized using descriptive statistics as separate categories by study product group. Total number of brushings is defined as: [(date of last brushing – date of first brushing + 1) multiplied by 2 – number of missing brushings + number of additional brushings]. Compliance (%) is defined as: [100 x (Total number of brushings / Expected number of brushings)], where expected number of brushings is defined as: [(date of last brushing - date of first brushing + 1) multiplied by 2].

Study product brushing compliance (total number of brushings / compliance (%) / missed brushings / additional brushings) will be listed in [Listing 16.2.5.1](#) for all randomized subjects by study product groups.

On-site study product brushings will also be summarized for the mITT population in [Table 14.2.1.2](#) by visit. In addition, details (including subject number, date and start time of brushing) for on-site study product brushings will be listed ([Listing 16.2.5.2](#)) for all randomized subjects by study product group.

4.3.2 Prior and Concomitant Medication

Any medications, treatments or vaccine (including over-the-counter or prescription medicines, vitamins and/or herbal supplements) taken during the study, 30 days prior signing the informed consent, must be recorded in the eCRF with indication, reason for use, unit dose, daily dose and start/stop dates of administration. All subjects will be questioned about concomitant medication/treatments at each site visit.

Prior medication/treatments are defined as medication/treatments taken in the 30 days prior signing the ICF and before the first use of study product (i.e., assigned study toothbrush).

Prior medications will be listed by subject, with drug name, GSK drug synonym, reason, dose, frequency, route, start and end dates, study day relative to study product start and end date ([Listing 16.2.4.3](#)) by study product group for all randomized subjects.

Concomitant medications and concomitant non-drug treatments are defined as medications or non-drug treatment/procedures taken after first use of study product. Any medication, which are ongoing at the time of first use of study treatment will also be considered as concomitant.

Unknown dates will not be imputed. If the stop date is unknown, or incomplete, and the medication cannot be considered as stopped prior to the date of signing the ICF then the

medication will be considered as a concomitant medication (unless partial start or stop dates indicate differently).

Concomitant medications and concomitant non-drug treatments will be listed ([Listing 16.2.4.4](#)) similarly to prior medication with either ongoing or end date displayed by study product group for all randomized subjects.

4.4 Analysis of Efficacy

The mITT population will be considered as primary population for primary analyses.

4.4.1 Primary Efficacy Endpoint

4.4.1.1 Primary Efficacy Endpoint Definition

The main focus of the analysis will be the ability of each study toothbrush to reduce supra-gingival plaque after first use (Day 0, pre- to post-brushing), as measured by mean RPI overall and mean TPI overall.

For RPI, each tooth surface is divided into nine zones (A to I); A-C along the gingival margin; D-F directly above A-C (D and F being the inter-proximal zones); G-H across the middle of the tooth and I covers the incisal area. The plaque will be disclosed and the presence or absence of plaque in each zone recorded, generating a total of 18 scores per tooth. RPI scale is described in [Table 4-2](#) below.

Table 4-2 RPI Scoring

Score	Description
0	Plaque absent
1	Plaque present

For TPI, each tooth surface is divided into 3 areas; three scores are recorded facially (mesiofacial, facial, distofacial) and three scores lingually (mesiolingual, lingual and distolingual) generating a total of six scores per tooth.

The plaque will be disclosed and scored for each site as described in [Table 4-3](#).

Table 4-3 TPI Scoring

Score	Description
0	No plaque
1	Slight flecks of plaque at the cervical margin of the tooth
2	Thin, continuous band of plaque (1 millimetre (mm) or smaller) at the cervical margin of the tooth
3	Band of plaque wider than 1mm but covering less than 1/3 of the area
4	Plaque covering at least 1/3 but less than 2/3 of the area
5	Plaque covering 2/3 or more of the crown of the tooth

Mean RPI_{overall} and mean TPI_{overall} will be calculated for each subject as the total score for all tooth sites assessed divided by the total number of tooth sites assessed.

Change from baseline will be derived for each individual tooth site first before calculating the mean overall change for all sites assessed. Changes from baseline will be derived, summarized and analyzed.

Descriptive statistics (n, missing, mean, SD, standard error [SE], median, minimum, and maximum values) of the pre-brushing, post-brushing and change from Day 0 pre-brushing in mean RPI_{overall} and mean TPI_{overall} scores will be presented in [Table 14.2.2.1.1](#) for mean RPI_{overall} and in [Table 14.2.2.2.1](#) for mean TPI_{overall} for all subjects in mITT population by study product group.

The listings of RPI and TPI derived scores by subject will be presented for all randomized subjects ([Listing 16.2.6.1.1](#) for RPI derived scores and [Listing 16.2.6.2.1](#) for TPI derived scores). These listings will include subject number, visit, pre-brushing mean scores, post-brushing mean scores, change from pre-brushing to post-brushing and change from Day 0 pre-brushing.

All RPI index data collected in the eCRF will be listed in [Listing 16.2.6.1.2](#) for all randomized subjects while TPI index data collected in the eCRF will be listed in [Listing 16.2.6.2.2](#) for all randomized subjects.

4.4.1.2 Statistical Hypothesis, Model, and Method of Analysis

In this study, baseline is defined as the Day 0 pre-brushing mean plaque score for each index (RPI/TPI). Primary analysis will focus on the ability of each study toothbrush to reduce supra-gingival plaque after first use (Day 0, pre- to post-brushing).

Mean RPI_{overall} and mean TPI_{overall} will be calculated for each subject as the total score for all tooth sites assessed divided by the total number of tooth sites assessed. Change from baseline will be derived for each individual tooth site first before calculating the mean overall change for all sites assessed.

Plaque removal efficacy after first use (change from baseline) will be tested under the null hypothesis:

- H₀: there is no change from the baseline plaque level;
- H₁: there is a change from the baseline plaque level.

Change from baseline in mean RPI_{overall} and mean TPI_{overall} will be analyzed using analysis of covariance (ANCOVA).

Change from baseline will be summarized for each primary outcome variable by study product group (adjusted mean change, percent change from mean baseline, 95% confidence intervals [CIs] and p-value for change from zero). Percent change from mean baseline will be derived as: 100 x (Adjusted Mean Change / Mean Baseline Value). Adjusted Mean Change will be derived from ANCOVA model.

No formal sample size has been generated for this methodology development study, thus the p-values will be interpreted with caution.

For analysis of mean RPI_{overall}, the model will include product group as a fixed effect and the baseline mean RPI_{overall} value as a covariate (Table 14.2.2.1.2). RPI stratification level will not be used in the analysis as the actual value will be used as a covariate.

For analysis of mean TPI_{overall}, the model will include product group as a fixed effect, the baseline mean TPI_{overall} value as a covariate and RPI stratification level [lower (defined as Day 0 pre-brushing mean RPI_{gingival/interproximal} ≥ 0.6 to ≤ 0.8) or higher (defined as Day 0 pre-brushing mean RPI_{gingival/interproximal} > 0.8 to 1.0)] as an extra factor (Table 14.2.2.2.2).

Size of effect will be a point of focus. As this is a methodology development study, no adjustments will be made for multiple comparisons.

The assumption of normality and homogeneity of variance in the ANCOVA models will be investigated. Violation of this assumption will be overcome using a suitable data transformation or a non-parametric technique (e.g. Wilcoxon Sign Rank test).

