5.5 Lifestyle Considerations

If, in the opinion of the investigator or medically qualified designee, a subject has not complied with a study restriction prior to a study visit, re-appointment should be considered. The reason for re-appointment will be documented in the CRF. If re-appointment within permitted visit tolerances (Table 1-1 Schedule of Activities) or site availability is not possible, the following visit specific actions should be taken.

- **Visit 2:** the subject will be withdrawn from the study (Section 7.1). AEs will be recorded, and the OST examination completed; no clinical efficacy assessments will be performed. The subject may be replaced.
- **Visit 3:** the subject will continue in the study. AEs will be recorded, and the OST examination completed; no clinical efficacy assessments will be performed. The subject will not be replaced.
- **Visit 4:** the subject will be withdrawn from the study (Section 7.1). AEs will be recorded and the OST/OHT examinations completed; no clinical efficacy assessments will be performed. The subject will not be replaced.

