12.3.5 Secondary Analyses

Secondary outcome variables include change from baseline in:

- Mean RPI_{overall} (Day 7, Day 28)
- Mean TPI_{overall} (Day 7, Day 28)
- Mean RPI_{gingival margin} (Day 0, Day 7, Day 28)
Sites A, B and C will be used for calculations
- Mean RPI_{inter-proximal} (Day 0, Day 7, Day 28)
Sites D and F will be used for calculations
- Mean TPI_{inter-proximal} (Day 0, Day 7, Day 28)
Mesial and distal sites will be used for calculations

Secondary outcome variables will be derived, based on relevant tooth sites, as the primary outcome variables, with the following summaries generated and analyses performed.

Variable Calculation	Timepoint	Type of Analysis
Actual value	Day 0 (pre- and post-brushing)	Summary statistics

	Day 7 (pre- and post-brushing) Day 28 (pre- and post-brushing)	Plot of pre- and post-brushing values for Days 0, 7 and 30 Box plots
Change from baseline [Day 0 (pre-brushing)]	Day 7 (pre- and post-brushing) Day 28 (pre- and post-brushing)	Summary statistics Plot of change from baseline for Days 7 and 30 ANCOVA for within treatment comparisons

Summary statistics (number of subjects, mean, median, SE, SD, minimum, maximum) will be presented for each outcome variable at each assessment time point by treatment group.

For change from baseline calculations, baseline will be the mean Day 0, pre-brushing plaque score; percent change will also be presented and calculated as $100 \times (\text{Value} - \text{Baseline Value}) / \text{Baseline Value}$. This percent change will be calculated from the aggregated mean levels not at the individual subject level.

Actual mean plaque scores (\pm SE) for both indices will be plotted over time by treatment group. Pre-brushing values will be set at the nominal time recorded (Days 0, 7 and 28); post-brushing values will be set at a small nominal time after (Days 0.5, 7.5 and 28.5). Box plots will also be presented for each outcome variable, over time by treatment group

For variables to be formally analyzed to test for a significant change from zero, change from baseline will be analyzed using an ANCOVA model, with treatment as a fixed effect and the appropriate baseline value as a covariate, as per the primary analysis. For TPI analyses, an extra factor will be included for the RPI_{gingival/interproximal} stratification level (lower/higher). Adjusted mean changes, 95% CIs and p values for change from zero will be presented.

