1.1 Study Design

This will be a single center, 4-week, randomized, controlled, examiner-blind, four-treatment arm, parallel design, clinical methodology development study to investigate the plaque removal efficacy of marketed manual toothbrushes in healthy, dentate subjects. Changes in plaque level will be evaluated after first brushing, after two further single brushing events (Days 7 and 28) and following 7 and 28 days usage (twice daily brushing with assigned toothbrush product).

Supra-gingival plaque levels will be assessed using two established clinical measures:

- Rustogi-modification of the Navy Plaque Index (RPI), which focusses on plaque along the gingival margin and in the inter-proximal areas.
- 6-site Turesky modification of the Quigley and Hein Plaque Index (TPI), which focusses on plaque on the lower gingival third of the tooth surface.

Subjects will abstain from oral hygiene for a period of 12-18 hours prior to each assessment visit.

Clinical efficacy assessments will be performed at a single clinical site by a single dental examiner to eliminate inter-examiner variability. Intra-examiner variability will be monitored by performing repeat clinical assessments for both plaque indices, in randomly selected subjects, across the study period.

To ensure study subjects demonstrate the required propensity for plaque formation, only subjects with Day 0 pre-brushing mean RPI_{gingival/interproximal} ≥ 0.6 will be randomized to study product groups (Visit 2). Subjects will be stratified by their Day 0 pre-brushing RPI_{gingival/interproximal} score (lower: mean RPI_{gingival/interproximal} ≥ 0.6 to ≤ 0.8 ; higher: mean RPI_{gingival/interproximal} > 0.8).

gingival/interproximal > 0.8 to 1.0) to ensure study product groups are balanced for baseline supra-gingival plaque levels.

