1.2 Study Objectives

Study objectives and endpoints are defined in [Table 1-2](#):

Table 1-2 Study Objectives and Endpoints

Objectives	Endpoints
Primary	
To evaluate the within-treatment supra-gingival plaque removal efficacy of four manual toothbrushes after a single brushing event (first use).	Change from pre- to post-brushing in mean RPI - overall* (Day 0). Change from pre- to post-brushing in mean TPI - overall (Day 0). * all sites assessed
Secondary	
To evaluate the within-treatment supra-gingival plaque removal efficacy of four manual toothbrushes after single brushing events, following 7 and 28 days familiarization with the brush.	Change from baseline (Day 0 pre-brushing) to post-brushing in mean RPI and mean TPI - overall (Day 7, Day 28). Pre- and post-brushing mean RPI and mean TPI- overall (Day 7, Day 28).
To evaluate the within-treatment supra-gingival plaque removal efficacy of four manual toothbrushes at the gingival margin and from inter-proximal sites, after single brushing events, following 0, 7 and 28 days familiarization with the brush.	Change from baseline (Day 0 pre-brushing) to post-brushing in mean RPI and mean TPI - gingival margin sites (RPI only); inter-proximal sites (Day 0, Day 7, Day 28). Pre- and post-brushing mean RPI and mean TPI - gingival margin sites (RPI only); inter-proximal sites (Day 0, Day 7, Day 28).
To evaluate the within-treatment supra-gingival plaque removal efficacy of four manual toothbrushes after 7 and 28 days twice-daily brushing.	Change from baseline (Day 0 pre-brushing) in mean RPI and mean TPI - overall; gingival margin sites (RPI only); inter-proximal sites (Day 7 pre-brushing, Day 28 pre-brushing).
Safety	
To assess the safety and oral tolerability of the four manual toothbrushes after first use (Day 0) and over 28 days' use.	TEAEs

This clinical methodology development study will be considered successful if a numerical reduction in supra-gingival plaque levels is observed for each toothbrush after first use (Day 0, pre- to post-brushing), for both clinical measures.

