- [Table 14.2.2.3.2](#) for mean RPI_{gingival margin}
- [Table 14.2.2.4.2](#) for mean RPI_{inter-proximal}
- [Table 14.2.2.5.2](#) for mean TPI_{inter-proximal}

Percent change from mean baseline will be derived as: $100 \times (\text{Adjusted Mean Change} / \text{Mean Baseline Value})$. Adjusted Mean Change will be derived from ANCOVA model.

The assumption of normality and homogeneity of variance in the ANCOVA models will be investigated. Violation of this assumption will be overcome using a suitable data transformation or a non-parametric technique (e.g. Wilcoxon Sign Rank test).

Actual mean plaque scores (\pm SE) for all secondary efficacy endpoints will be plotted over time by study product group for all subjects in mITT population in the following figures:

- [Figure 14.2.2.1.1](#) for mean RPI_{overall}
- [Figure 14.2.2.2.1](#) for mean TPI_{overall}

-
- [Figure 14.2.2.3.1](#) for mean RPI_{gingival margin}
 - [Figure 14.2.2.4.1](#) for mean RPI_{inter-proximal}
 - [Figure 14.2.2.5.1](#) for mean TPI_{inter-proximal}

Pre-brushing values will be set at the nominal time recorded (Days 0, 7 and 28), while post-brushing values will be set at a small nominal time after (Days 0.5, 7.5 and 28.5).

All RPI index data collected in the eCRF will be listed in [Listing 16.2.6.1.2](#) for all randomized subjects while TPI index data collected in the eCRF will be listed in [Listing 16.2.6.2.2](#) for all randomized subjects.

The listings of derived scores of secondary efficacy variables by subject will be presented for all randomized subjects as follows:

- [Listing 16.2.6.1.1](#) for mean RPI_{overall}
- [Listing 16.2.6.2.1](#) for mean TPI_{overall}
- [Listing 16.2.6.1.3](#) for mean RPI_{gingival margin}
- [Listing 16.2.6.1.4](#) for mean RPI_{inter-proximal}
- [Listing 16.2.6.2.3](#) for mean TPI_{inter-proximal}

These listings will include subject number, visit, pre-brushing mean scores, post-brushing mean scores, change from pre-brushing to post-brushing, and change from Day 0 pre-brushing.

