4.7 Analysis of Other Variables

Additional/Exploratory endpoint for this study is to analyze the repeatability of dental plaque scoring.

The clinical examiner selected for this study will have demonstrated their ability to replicate their own scores (intra-examiner repeatability) on a tooth site-by-tooth site basis. Given both the RPI and the TPI allow accurate repeat assessment, repeat assessments will be performed for both clinical measures throughout the treatment period (Visits 2 to 4) to monitor consistency of scoring.

One repeat assessment will be completed for each clinical index on each clinical assessment day (one in the morning, one in the afternoon), alternating between pre- and post-brushing assessments for each index. Repeatability assessments should be separated by a minimum of 10 minutes and, where possible, the clinical examiner should assess a different subject in the intervening period. The examiner should not have sight of their previous scores when carrying out a repeat assessment.

‘Repeat’ subjects will be selected from those in attendance on a particular study day.

The repeat dental plaque assessments (for both RPI and TPI indices) will be compared to the original assessments. Repeat assessments will not be used in any efficacy analyses.

The first and repeat plaque assessments on each tooth site will be cross tabulated. A weighted kappa coefficient (κ), along with the 95% CI will be calculated to assess the intra-examiner reliability.

Fleiss-Cohen weighted kappa will be calculated for the repeatability analysis. Reliability will be deemed

- excellent if $\kappa > 0.75$;
- fair to good if $0.4 \leq \kappa \leq 0.75$;
- poor if $\kappa < 0.4$.

A $\kappa \geq 0.6$ will be considered indicative of good repeatability across the study period.

Repeatability analysis will be conducted on RPI Repeatability and TPI Repeatability Populations.

Results for RPI scoring repeatability will be presented in [Table 14.2.3.1](#). Results for TPI scoring repeatability will be presented in [Table 14.2.3.2](#).

5 Changes to the Protocol Defined Statistical Analysis Plan

Any changes from the originally planned statistical analysis specified in the protocol are outlined in [Table 5-1](#).

Table 5-1 Changes to Protocol Defined Analysis Plan

Protocol	Reporting & Analysis Plan	
Statistical Analysis section	Statistical Analysis Plan	Rationale for Changes

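### Does the undefined baseline mean in the SAP's percent-change formula call for a change to the plan?

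*SAP*

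**What the plan says.** SAP 4.4.1.2 introduces the primary summary with "Change from baseline will be summarized for each primary outcome variable by study product group". The items reported are the adjusted mean change, a percent change, a 95% confidence interval and a p-value against zero. It then defines the percentage: "Percent change from mean baseline will be derived as: 100 x (Adjusted Mean Change / Mean Baseline Value". SAP 4.5.1 repeats the formula for the secondary outcomes and adds that "Adjusted Mean Change will be derived from ANCOVA model".

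Baseline is fixed by time point and index as the Day 0 pre-brushing score (SAP 3.1 and 4.4.1.2). Four things are not written:

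- whether the mean is by product group or pooled;
- the baseline value at which the adjusted mean is taken;
- which subjects the mean covers at Days 7 and 28;
- how the two strata are weighted in the TPI model.

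Protocol 12.3.5 defines percent change for the secondary outcomes as 100 x (Value - Baseline Value) / Baseline Value, and adds: "This percent change will be calculated from the aggregated mean levels not at the individual subject level". Protocol 12.3.4, on the primary analysis, gives no percent-change formula.

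SAP section 5 says of Table 5-1: "Any changes from the originally planned statistical analysis specified in the protocol are outlined in" that table. Its three rows cover the split of the repeatability population and two dropped plot types. Percent change is not among them.

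**The concern.** An ANCOVA adjusted mean is conventionally evaluated at the pooled baseline. If it is then divided by the brush's own baseline mean, numerator and denominator refer to different baselines. The percentage is multiplied by pooled/arm baseline, which puts back some of the imbalance that the model removed. A brush whose users happened to start with less plaque would appear to remove a larger share.

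The SAP names size of effect as a point of focus, and the protocol's own benchmark from the literature is a percentage (30-53% removal after one brushing). Readers may well compare brushes on this scale, and the results may inform later studies. A formula that can be read two ways, differs from the protocol and is not logged as a change therefore looks like something to correct.

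**Working it through.** The documents contain no percent change, baseline mean or SD, so there is no planned figure to reproduce.

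**Three readings.** Let x_i be the arm baseline mean, x the pooled baseline mean, raw_i the mean change in arm i, b the ANCOVA slope, and adj_i = raw_i - b(x_i - x).

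- A: 100 x adj_i / x_i (adjusted change over own-arm baseline)
- B: 100 x adj_i / x (adjusted change over pooled baseline)
- C: 100 x raw_i / x_i (the protocol formula)

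It follows that A = B x (x / x_i). All three agree when arm baselines are equal.

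**Worked cases**, using the ends of the protocol's 30-53% range and an assumed arm baseline 10% away from the pooled mean, with removal proportional to baseline:

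| True removal | Arm baseline | A | B | C |
|---|---|---|---|---|
| 30% | 10% low | 30/0.9 = 33.3 | 30.0 | 30.0 |
| 30% | 10% high | 30/1.1 = 27.3 | 30.0 | 30.0 |
| 53% | 10% low | 53/0.9 = 58.9 | 53.0 | 53.0 |
| 53% | 10% high | 53/1.1 = 48.2 | 53.0 | 53.0 |

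If change does not depend on baseline (b = 0), A equals C and only B differs. No reading is best under every pattern.

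**How large chance imbalance is likely to be.** Assume baseline mean 0.65, SD 0.08 or 0.12, 40% removal, 20 per arm and 80 in all. Without stratification, the SD of A minus B is approximately 40 x (SD/0.65) x sqrt(1/20 - 1/80):

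- SD 0.08: 40 x 0.123 x 0.194 = 0.95 points
- SD 0.12: 40 x 0.185 x 0.194 = 1.43 points

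Simulation gives 0.96 and 1.44. But the trial stratifies on a closely related score "to ensure study product groups are balanced for baseline supra-gingival plaque levels". Simulating that (4000 trials per setting, blocks of 4 within stratum, correlation 0.9 between the stratifying score and overall RPI, residual SD 0.04, 10-50% of subjects in the lower stratum, all assumed) lowers the SD to 0.68-1.24 points, with a 95th percentile of 1.3-2.5.

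**What that adds to ordinary noise.** In the same simulation the four brushes are identical. The mean range of the four percentages is 3.25-4.10 points on reading A and 2.83-2.89 on reading B. Reading A therefore adds roughly 0.4 (3.25 - 2.83) to 1.2 (4.10 - 2.89) points to a spread of about 2.8 that is present either way. With residual SD 0.06 the ranges are 4.5-5.2 and 4.2-4.3.

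**What cannot move.** The adjusted mean change, its interval and its p-value are computed before any division. The study "will be considered successful if a numerical reduction in supra-gingival plaque levels is observed for each toothbrush after first use", on both indices. That criterion rests on the sign of the change, and dividing by a positive baseline leaves the sign alone. RPI baselines are well above zero: entry requires a mean of at least 0.6 over 10 of the 18 zones per tooth, so with all zones scored the overall mean is at least 0.6 x 10/18 = 0.33.

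**Can a reader recover the other version?** Yes for Day 0. The adjusted changes appear in Tables 14.2.2.1.2 and 14.2.2.2.2, and the pre-brushing means with n by product group in Tables 14.2.2.1.1 and 14.2.2.2.1. The pooled mean is the n-weighted average of the group means.

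**The case for a change.** The best case for changing the plan is that the likely reading, own-arm, is the one that mixes two baselines, and that readers will rank brushes on the percentage. Without stratification and with no true difference between brushes, the order of the four differed between readings A and B in 43-79% of simulated trials (baseline CV 10-20%, removal 30-53%). The largest A-B gap over the four brushes had a 95th percentile of 1.5-5.3 points. The algebra stands. The order of four identical brushes is noise on any reading, though, and the plan makes no between-brush comparison. For a percentage reported brush by brush, the brush's own baseline is a natural denominator.

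A second point is the subject set. For a restriction breach at Visit 3 or 4 that cannot be re-appointed, Protocol 5.5 says "no clinical efficacy assessments will be performed. The subject will not be replaced". The baseline mean of all mITT subjects and that of subjects in the model can then differ at Days 7 and 28. This is true but has not been sized, since no rate of missing visits is given. It should barely touch the primary endpoint, which is assessed shortly after randomization. SAP 4.1.3 refers to Attachment 1 for the population used in each display, and that list is not reproduced here.

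A third is that the change is unlogged. It is, but the formula is stated openly in two SAP sections. Protocol 12.2 leaves further detail to the analysis plan, and an adjusted mean is itself an aggregate, so the conflict with 12.3.5 is one of detail.

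Prescribing a pooled denominator with TPI adjusted means at observed stratum proportions would not be a neutral repair. Relative to equal weights, it would shift the primary TPI adjusted change by |q - 0.5| x g, where q is the share in one stratum and g the stratum difference as a percentage of baseline. With q = 0.70 and g = 5 that is 1.0; with q = 0.85 and g = 10 it is 3.5 (both assumed). The interval and p-value would move too. That can exceed the ambiguity it is meant to cure.

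**Conclusion.** No change to the plan follows. The SAP leaves a definition unwritten, and an analyst following the layout by product group would fill it sensibly with the brush's own Day 0 mean and say so in the table footnote. The absence of a Table 5-1 row is a clerical slip. On the stated assumptions, with stratified allocation, the choice of denominator moves a descriptive percentage by an SD of about 0.7-1.2 points. The shift would be larger with more variable baselines or removal nearer 53%. Either reading leaves the adjusted changes, intervals, p-values and success criterion as they are. The pooled denominator is a defensible preference, but the protocol's raw-mean formula does as well when removal is proportional to baseline (mean range 2.82-2.88 points against 2.83-2.89). There is no clear gain in requiring one over the other.
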